## 5. TIMELINE OF THE STUDY

The study includes the period of early mobilization by robotic system of patients who meet the inclusion and exclusion criteria. These will be mobilized using the robotic early mobilization device twice a day for 20 minutes, at least ten times or within seven days. The data collection is planned for five to six months.

Within the study period, the following topics will be covered in three study lines (cf. fig. 4):

- (1) Feasibility of robot-assisted VEM in the Intensive Care Unit.
- (2) Behavior and experience of the mobilizing professionals
- (3) Effects on patients outcomes.

[figure not shown]

Figure 4: Overview of the time courses of the study arms.

## 6. STUDY DESIGN

The present study is a monocentric, prospective intervention study, designed to

- evaluate the feasibility and integration in the setting of an Intensive Care Unit.
- evaluate the behavior and experience of the mobilizing specialists of the robot-assisted VEM in a longitudinal section (three data collection points).
- compare robot-assisted VEM in critically ill intensive care patients with non-robot-assisted early mobilization according to the standard of care of a historical patient population.

## 7. STUDY POPULATION

The study population consists of adult patients undergoing surgical procedures and scheduled for postoperative treatment in the anesthesiological intensive care units at LMU Klinikum, with an Clinical intervention study – Project MobiStaR

anticipated postoperative ventilation duration of > 48 hours. All patients will be included in the prospective intervention study according to inclusion and exclusion criteria.

Feasibility surveys will be conducted by project staff and will refer to the study populations of patients and mobilizing professionals.

The mobilizing professionals consist of physicians, nurses and physiotherapists working in anesthesiological intensive care units, who are regularly involved in mobilization. Physicians, nurses and physiotherapists will be included according to inclusion and exclusion criteria.

## 7.1 INCLUSION AND EXCLUSION CRITERIA FOR PROFESSIONALS INVOLVED

### *Inclusion Criteria*

Nurses with advanced training in anesthesia and intensive care and/or nurses who have at least three years of professional experience in an intensive care unit will be included. In addition, these persons have an employment contract at LMU Hospital.

Similarly, specialists in leading positions in intensive care units with completed residency training and an employment contract at LMU-Klinikum as well as physiotherapists with at least three years of professional experience in an intensive care unit and an employment contract at LMU-Klinikum are included.

For T2 and T3, all specialists should also be assigned to the anesthesiological intensive care units.

Specialists will only be included if they agree to participate in the study.

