- (2) The behavior and experience of the mobilizing professionals will be evaluated using episodic interviews as well as standardized observations. Nurses with specialized training in anesthesia and intensive care, nurses and physiotherapists who have at least three years of professional experience in an intensive care unit as well as medical specialists who have completed their training as medical specialists or who have a leading position in an intensive care unit are included. In addition, the individuals have an employment contract at LMU Klinikum. Furthermore, the secondment to the anesthesiological intensive care units is an inclusion criterion.
- (3) The effects on patient outcomes, primarily duration of ventilation, muscle mass (sonographic examination) and physical activity (measured by established scores such as FSS-ICU and MRC classification), will be measured at different points in time and compared with a historical patient population. Secondary outcomes such as delirium incidence, hemodynamic parameters, respiratory parameters but also longitudinal parameters such as intensive care and hospital length of stay will be analyzed from routine data/patient records. Included are informed consenting patients who will undergo a planned surgical procedure that involves postoperative intensive treatment and an anticipated duration of ventilation of more than 48 hours. These patients will receive standardized early mobilization using the robotic system at either ten frequencies or for seven days. No invasive procedures such as blood sampling will be performed as part of the study. To evaluate the effect of robot-assisted VEM, the outcomes

will be compared with a historical comparison group. Approximately 30 patients shall be included. The results will be compared to a historical group (n=30) with conventional early mobilization.

The intervention is planned for a duration of five to six months starting in August 2021.

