### *Exclusion criteria*

Persons who are members of the MobiStaR project team, have less than three years of professional experience as a nurse or specialist in an ICU, or are still in residency training are excluded. Physiotherapists with less than three years of professional experience in intensive care units are also excluded. Individuals who are not employed at LMU Hospital are also excluded. In T2 and T3, specialists who are not assigned to the anesthesiological intensive care units according to the duty schedule are excluded.

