## 8. METHOD AND PROCEDURE

Patients of the LMU Hospital will be included according to the inclusion and exclusion criteria (see 5.2. and 5.3.). All patients who are to be treated surgically and whose postoperative care is planned in the anesthesiological intensive care units will be screened according to the inclusion and exclusion criteria. If the expected duration of postoperative ventilation exceeds 48 hours and there are no contraindications, the patient is given an information session. This should be done preoperatively with awake patients who are able of giving consent. In case of consent, the patient will be included in the study.

In addition, within the scope of the experience of the mobilizing specialists, nurses, physiotherapists, and physicians will be included according to inclusion and exclusion criteria, who are predominantly assigned to the intensive care units of the LMU Hospital and from T2 onwards to the anesthesiological intensive care units.

With the start of robot-assisted early mobilization, the survey will be conducted within the framework of organizational feasibility. This is carried out by project staff and ward staff. The survey ends with the last robot-assisted mobilization.

[figure not shown]

Fig. 5: Detailed procedure of the study with examination times of the patients

All patients will receive a physical examination at different time points to assess physical functionality and muscle strength, as well as a sonographic examination of leg muscles, diaphragm, and lungs. These examinations should be performed on day -1 (preoperatively), on postoperative days 1,2,3, then once a week if the patient remains in the Intensive Care Unit, on day 28, on the day of discharge from the Intensive Care Unit, and on a follow-up examination approximately 3 months after discharge from the Intensive Care Unit. The follow-up examination should only take place if the patients present themselves at the LMU Hospital anyway due to medically indicated follow-up examinations (not study-related). Alternatively, patients can be asked about their condition by telephone (see Fig. 5).

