## 2. Survey of positioning and mobilization behavior

- Standardized observations (50) with n= 30-50
  - o Analysis by means of descriptive statistics (51)
  - o Behavior and attitude of mobilizing professionals will be observed (see appendix for topics of observation)
  - o In addition, the following data will be included in T2 and T3, which will be collected in the study arm "effects on patient outcomes":
    - o Ventilation (Yes / No)
    - o Medication (in Weaning → Yes / No; Analgosedation → Yes / No; Catecholamines → Yes / No )
    - o Gender
    - o Weight/ Height

Observation will only occur during mobilization of patients who have given consent to participate in the study.

Additionally, only mobilizing professionals who have given consent to participate in the study will be included in the observations and interviews. Should consent to the study be subsequently withdrawn at a later date, the study participants will be asked whether the data obtained up to that point may still be used. Otherwise, all the data collected up to that point will be destroyed.

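### The staff unit restriction applies only at T2 and T3, so the contrast of T1 (no robot) with T2/T3 (robot) can mix the robot with a change of unit, most clearly in the interviews

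*Protocol*

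**What the plan says.** **Staff eligibility.** Section 7.1 sets general criteria for nurses, physicians and physiotherapists: ICU training, experience or position, and employment at the hospital. For nurses it reads "nurses who have at least three years of professional experience in an intensive care unit will be included", with advanced training as the other route. None of these criteria names a particular unit. A separate sentence, limited to T2 and T3, adds that "all specialists should also be assigned to the anesthesiological intensive care units". The exclusion criteria mirror it, again for T2 and T3 only: "specialists who are not assigned to the anesthesiological intensive care units according to the duty schedule are excluded". Section 8 describes staff "who are predominantly assigned to the intensive care units of the LMU Hospital" and brings in the anesthesiological units only from T2 onwards.

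Two places read differently. The executive summary says that "the secondment to the anesthesiological intensive care units is an inclusion criterion", and section 7 says "The mobilizing professionals consist of physicians, nurses and physiotherapists working in anesthesiological intensive care units". Neither limits the condition to a time point.

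**The contrast.** Section 4.2 lists emotions, motivating and challenging factors, physical strain, behavior, posture and personnel effort, each recorded without the robot at T1 and with it at T2 and T3. One of its research questions asks what introducing the robot does to staff behavior. Section 6 calls this component longitudinal, with three collection points.

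**Patient data.** Section 8.2 restricts observation to mobilizations of consenting study patients. It then says "In addition, the following data will be included in T2 and T3" and lists ventilation, weaning, analgosedation, catecholamines, gender and weight/height, taken from the patient-outcomes arm. The table in section 4.2 has the same T2/T3 limit.

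**The concern.** A before/after contrast can inform about the robot only if little else changes between the two periods. Here a stated eligibility rule differs between exactly those periods: the robot-free time point is the only one open to staff from other ICUs. Units may differ in patients, staffing and mobilization routine, so a change in reported strain or in the number of staff needed could reflect the unit as well as the device.

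The experience and behavior of staff is one of the three study aims. A purely descriptive T1 v T2/T3 difference will still be read as a consequence of the robot, because the protocol poses that question. An analysis plan could not repair this later: eligibility is fixed when staff are recruited, and patient characteristics not recorded at T1 may not be recoverable.

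**Working it through.** The protocol gives no figure for this point, so the check is a comparison of the text, first for staff and then for patients.

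**Step 1: which units may supply staff?**

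| Place in the protocol | T1 | T2 and T3 |
|---|---|---|
| 7.1, inclusion | no unit named | anesthesiological ICUs |
| 7.1, exclusion | no unit-based exclusion | staff outside the anesthesiological ICUs excluded |
| 8 | the hospital's ICUs generally | anesthesiological ICUs |
| 1 (executive summary) | anesthesiological ICUs | anesthesiological ICUs |
| 7 | anesthesiological ICUs | anesthesiological ICUs |

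Three statements agree that T1 is wider, and two say it is not. The first three are the operative eligibility and procedure text and name the time points, so the split looks deliberate. All five cannot govern T1 recruitment together.

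**Step 2: does the difference fall on the contrast of interest?** Yes. In section 4.2, T1 is without the robot and T2/T3 are with it. The wider rule applies at T1 only, so under section 7.1 a change of unit can coincide with the arrival of the robot.

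**Step 3: interviews.** Section 8.2 asks for at least four people per professional group, until saturation, with a distress thermometer at each interview. With three groups the minimum is 4 × 3 = 12 people; the text does not say whether this is per time point. No patient rule applies to the interviews, and nothing requires the same people or units at T1 and later. The unit problem is therefore open here.

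**Step 4: observations.** Only consenting study patients may be observed. Sections 7 and 8 draw these patients from people whose postoperative care is planned in the anesthesiological ICUs. Read literally, this keeps observations in those units at every time point. But the same patients are enrolled to receive the robot, and the only comparison group the protocol defines is historical, selected retrospectively from routine data, so it cannot be observed. The protocol does not say whose robot-free mobilization is watched at T1. Section 9 adds to the doubt by describing the stress and physical-behavior data as collected within a robot-assisted mobilization. Whether the unit problem reaches the observations is therefore uncertain.

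**Step 5: can a shift in patient mix be seen?** The listed characteristics are linked only at T2 and T3. On the protocol's text there is nothing to set beside them at T1.

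**Step 6: what size could it have?** The protocol gives no basis for an estimate. As an illustration on assumed values only, let a share f of T1 data on a quantitative item come from other units that differ by d standard deviations. With no robot effect at all, the T1 v T2/T3 difference shifts by f × d:

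- f = 0.25, d = 0.3: 0.25 × 0.3 = 0.075 SD
- f = 0.75, d = 0.8: 0.75 × 0.8 = 0.60 SD

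The sample size does not enter the formula, so more observations would not reduce the shift.

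**The case against.** The best defense is that the text permits mixing but does not show it. T1 staff may all turn out to work in the anesthesiological ICUs, as the summary and section 7 say, and a longitudinal design may mean the same people are followed. This stands: a reader might infer that the comparison does mix units, and the document does not support that.

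The consent rule for observations also carries weight. A reader might infer that all T1 observations could come from units that supply no T2/T3 data, and might take the planned 30-50 observations as the T1 count. The rule points the other way, and section 8.2 does not say whether 30-50 is per time point or in total.

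A reader might also infer that workload is recorded only with the robot. It is not: personnel effort, posture and behavior are recorded at all three time points, and only the patient characteristics are limited to T2/T3. The observation topics are in an appendix that is not at hand, so the T1 sheet may already hold some patient items.

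Finally, this component is qualitative and descriptive. Two of its three research questions, on experience of the robot and on rated burden and relief, can be answered largely from T2 and T3. An uncontrolled before/after series carries time and learning effects even in a single unit. That lowers the stakes, but it does not justify adding an avoidable difference in units to the question that depends most on T1.

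**Conclusion.** The concern holds in a limited form. The operative criteria allow the robot-free time point to draw staff from a wider set of units than the robot time points, and two other places contradict this. The contrast in section 4.2 can therefore mix the robot with a change of unit. This is clearest for the interviews and uncertain for the observations, where the T1 patients are undefined and a difference in patient mix could not be described.

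The conclusion assumes that sections 7.1 and 8 govern recruitment; if the executive summary and section 7 govern, the staff part falls away and only the contradiction remains. It also assumes that the T1 observation sheet does not already capture the patient items.

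The size of any bias is not estimable from the protocol; the 0.075 to 0.60 SD above rests wholly on assumed inputs. The comparison of patient outcomes with the historical group is not affected. The point is worth correcting because the remedy is cheap, but it does not undermine the study as a whole.

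**What to change.** 1. Reconcile the executive summary and section 7 with sections 7.1 and 8, and use one unit criterion for staff at T1, T2 and T3.
2. If T1 is already complete, limit the T1 v T2/T3 contrast to staff or units seen at both times. If that is not possible, report the contrast as not attributable to the robot alone.
3. State in section 8.2 which patients are observed at T1, and align the description in section 9 with it.
4. Where those patients' consent covers it, record at T1 the same characteristics as at T2 and T3: ventilation, weaning, analgosedation, catecholamines, gender and weight/height.

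The main cost is a smaller pool of T1 staff. Items 1 and 3 are mostly wording. Item 4 needs a few fields on the T1 sheet if they are not there already, and it depends on first defining a consenting T1 patient group. Even with these changes the contrast remains an uncontrolled before/after comparison, and the report should say so.

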### *Exclusion criteria*

Persons who are members of the MobiStaR project team, have less than three years of professional experience as a nurse or specialist in an ICU, or are still in residency training are excluded. Physiotherapists with less than three years of professional experience in intensive care units are also excluded. Individuals who are not employed at LMU Hospital are also excluded. In T2 and T3, specialists who are not assigned to the anesthesiological intensive care units according to the duty schedule are excluded.

## 7.2 INCLUSION AND EXCLUSION CRITERIA FOR PATIENTS

### *Inclusion criteria*

- planned surgical intervention
- postoperative intensive care and therapeutic treatment
- expected duration of ventilation > 48 hours
- age ≥ 18 years
- preoperative patient consent for the study
- weight >45 kg and <135 kg

- Body height >1.50 m and <1.95 m

#### *Exclusion criteria*

- Patients refusal to participate in the study
- unable to give informed consent
- chronically bedridden before inclusion
- clinical frailty scale  $\geq 7$  (42)
- chronic ventilation (more than 24 hours) before admission to the intensive care unit
- Elevated intracranial pressure / risk for elevated intracranial pressure / recent cerebral hemorrhage
- Pregnancy
- Pre-existing neuromuscular disease resulting in chronic limitation of strength and performance
- Sternotomy / Sternectomy during a surgical procedure

Patients meeting the following criteria will be retrospectively selected for the historical comparison group:

- planned surgical procedure
- Postoperative intensive care and therapeutic treatment
- Duration of ventilation > 48 hours
- age  $\geq 18$  years
- Weight >45 kg and <135 kg
- Body height >1.50 m and <1.95 m
- Patients who met any of the exclusion criteria during their intensive care unit stay will not be included in the historical group.

No matching is planned.

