## 4.3 EVALUATION OF THE EFFECTS ON PATIENT OUTCOMES

- Can robot-assisted early mobilization improve muscle strength and reduce muscle loss compared with the historical collective?
- Can robot-assisted early mobilization reduce the duration of ventilation?  
In addition, further questions will be addressed:
- Does robotic-assisted early mobilization result in changes in consciousness, pain, cognition, health perception, cardiocirculatory and respiratory function, other factors such as pressure ulcers, bowel emptying, insulin requirements, and duration of treatment?

For this purpose, the following outcome criteria of the patients are examined.

Primary outcome criteria	Physical function/muscle strength	Surveyed according to the MRC (Medical Research Council) classification on upper and lower extremity and using the FSS-ICU (32, 33) at discharge ICU.
	Parameters for the assessment of muscle deterioration	Muscle thickness of quadriceps femoris muscle (thickness quadriceps femoris muscle and cross sectional area rectus femoris muscle)  Muscle thickness of the diaphragm / Thickening fraction diaphragm  Diaphragm mobility at discharge ICU
	Ventilation time	Duration (d) of invasive ventilation

Secondary outcome criteria	Consciousness/ cognition/ pain/ health perception	Pain using the Visual Analog Scale (VAS) (before and after mobilization).  Delirium incidence using the CAM ICU (34): number of days without delirium.  Sedation level using the Richmond Agitation Sedation Scale (RASS)(35)  level of consciousness using the Glasgow Coma Scale (GCS) (36)  Health-related quality of life after 3 months using the SF-36 questionnaire (37)
	Hemodynamics	Blood pressure / catecholamine demand / heart rate / cardiac output / oxygen consumption
	Respiration	CPAx-respiratory function(38) / oxygenation index / lung ultrasound parameter
	Others	Intestinal evacuation (yes/no)  Decubitus (grade classification 1-4 according to Shea (39))  Lactate level before and after mobilization (if laboratory value available)  Insulin requirement
	ICU Scores	SOFA [39] / Apache II (40) / SAPS II (41)  Intensive care unit treatment duration / inpatient treatment duration

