#### Conventional early mobilization

The comparison group is a historical collective, which also meets the inclusion and exclusion criteria of the study. These patients were early mobilized following the ward routine of the intensive care units conventional early mobilization according to the instructions of the treatment team, consisting of physicians, nurses, and physiotherapists. Conventional early mobilization cannot be precisely defined on the basis of a retrospective study (45, 15). The information used for the study regarding early mobilization and the defined outcome criteria of the patients is taken from the routinely collected data.

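### Historical controls must actually have been ventilated for more than 48 h, robot patients only be expected to be, so the primary outcome ventilation time has a floor in the control group alone

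*Protocol*

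**What the plan says.** **Robot group.** Four places in the protocol define entry by a forecast:

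- Section 1 (Executive summary): "postoperative intensive treatment and an anticipated duration of ventilation of more than 48 hours".
- Section 7 (Study population): "anticipated postoperative ventilation duration of > 48 hours".
- Section 7.2, inclusion criteria: "expected duration of ventilation > 48 hours".
- Section 8 (Method and procedure), at screening before surgery: "If the expected duration of postoperative ventilation exceeds 48 hours and there are no contraindications, the patient is given an information session".

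No section requires that a robot patient was in fact ventilated for more than 48 h.

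**Historical group.** Section 7.2 lists separate criteria for retrospective selection. Planned surgery, intensive care, age, weight and height are carried over. The ventilation item becomes "Duration of ventilation > 48 hours", without the forecast. The same section rules out matching. Section 8 (Conventional early mobilization) nevertheless says: "The comparison group is a historical collective, which also meets the inclusion and exclusion criteria of the study".

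**Outcome.** Section 4.3 asks "Can robot-assisted early mobilization reduce the duration of ventilation" and lists "Duration (d) of invasive ventilation" among the primary outcome criteria.

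**The concern.** The variable used to select the controls is, in substance, one of the variables on which the groups are compared. A control needs more than 2 days of ventilation to be in the data set. A robot patient who was expected to need more than 48 h but is extubated after 30 h stays in and contributes 1.25 days. The historical counterpart of that patient is never selected.

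There is a second effect. The control rule, as listed, also accepts patients whose ventilation was expected to be short and became long through an unforeseen course. The robot criterion would not have enrolled them.

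At stake is the ventilation question of section 4.3. Section 10 names ventilation time first among the things the patient comparison is meant to determine, and foresees quick uptake in routine care if the robot proves superior. Under two different entry rules, neither a difference in ventilation time nor its absence can be attributed to the device. The feasibility and staff-experience parts are not affected.

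**Working it through.** **What the protocol supplies.** About 30 robot patients and 30 controls (section 1), and the two entry rules above. It gives no distribution of ventilation time and no figure for q, so there is no stated figure on this point to reproduce. It names no test; section 9 promises only robust methods. Everything below apart from the group sizes and the 2-day limit is therefore an assumption.

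**Step 1: the floor alone, exact.** Suppose both groups come from one population and the device does nothing. The robot mean is then the overall mean, and the control mean is the mean of those above 2 days. Hence

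control mean − robot mean = q × (mean of those > 2 d − mean of those ≤ 2 d),

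which is positive whenever q > 0.

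**Step 2: numbers.** Take log-normal times with log-SD s and P(T ≤ 2 d) = q, and write z for the normal quantile of q. Then

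- μ = ln 2 − s·z
- overall mean m = exp(μ + s²/2)
- mean above 2 d = m·Φ(s − z)/(1 − q)

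Example with q = 10%, s = 0.8: z = −1.282, μ = 0.693 + 1.025 = 1.718 (median 5.6 d), m = exp(2.038) = 7.68 d. The mean above 2 d is 7.68 × 0.981/0.90 = 8.37 d. The difference is 8.37 − 7.68 = 0.69 d. As a check with Step 1, the mean at or below 2 d is 1.44 d, and 0.10 × (8.37 − 1.44) = 0.69 d.

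**Step 3: false-positive rates.** Simulation with no true effect, 30 vs 30, two-sided 5%, controls truncated above 2 d, log-SD 0.6 to 1.0. There were 10,000 replicates per cell for the rank test and 4,000 for the regressions. The regressions contain group plus 5 covariates unrelated to the outcome, which makes the 6 predictors that section 7.3 names as the maximum.

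| q (assumed) | Underlying median, log-SD 0.8 | Spurious mean benefit, log-SD 0.8 (range over 0.6–1.0) | Rank test | Regression, log days | Regression, days |
|---|---|---|---|---|---|
| 5% | 7.5 d | 0.46 d (0.25–0.83) | about 6% | 6–8% | 4–6% |
| 10% | 5.6 d | 0.69 d (0.40–1.17) | about 10% | 11–12% | 6% |
| 20% | 3.9 d | 1.01 d (0.62–1.60) | about 26% | 29–30% | 11–15% |
| 30% | 3.0 d | 1.24 d (0.79–1.88) | about 52% | 55–56% | 19–31% |
| 40% | 2.5 d | 1.43 d (0.94–2.09) | about 77% | 79–80% | 34–51% |

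From q = 10% upwards the false rank-test results are almost all in favour of the robot. At q of 5% or less the rates stay close to nominal.

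**Step 4: unforeseen controls.** Illustration at q = 10% with half the controls unforeseen, log-SD 0.6 to 1.0, no true effect:

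- Mostly just above 48 h (underlying median 0.75 d, kept only above 2 d): control minus robot is −1.06 to −3.43 d, against the robot; rank-test rejection 28–37%.
- Long-stayers (underlying median twice that of expected patients, kept only above 2 d): +2.82 to +6.80 d, for the robot; rejection 39–66%.

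The mixing share and both medians are invented. The point is only that the sign can go either way.

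**Step 5: does anything else in the protocol repair it?**

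- Section 7.4 permits exclusion for a criterion found to be violated, or for incomplete data. It is optional, and a forecast that proves wrong does not violate a criterion about expectation. Dropping early-extubated robot patients as incomplete would itself select on the outcome.
- The regression of section 7.3 adjusts for covariates. It cannot restore outcome values that were never sampled in one group, as the table shows.
- The statement in section 8 that controls meet the study criteria conflicts with the list in section 7.2 on this item.

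**The case against.** The strongest points on the other side are these.

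- **Ventilation versus invasive ventilation.** The control criterion does not say invasive; the outcome does. If non-invasive support counts towards the 48 h, a control could have fewer than 2 invasive days, and the floor is softer than modelled. This stands as a caveat. The asymmetry remains.
- **Section 8 may mean both rules apply.** If controls must have been expected to need, and have actually had, more than 48 h, there are no unforeseen controls and Step 4 falls away. The floor of Steps 1 to 3 remains in full.
- **q is unknown and may be small.** This is correct. At q of 5% or less the floor hardly matters, and rates above 50% need about 30% of the forecasts to be wrong. But nothing in the protocol bounds q.
- **The method is not fixed.** Section 9 names only robust methods, so the regressions are an illustration drawn from the sample-size section. The rank test is one plausible reading of section 9 and shows the same pattern.
- **A historical, unmatched comparison is limited anyway.** This is true, and section 10 itself urges caution in generalising the results. But general confounding does not excuse a truncation of the outcome that the selection rule creates and that can be avoided.
- **Routine records may not hold a preoperative forecast.** The protocol does not say whether they do. This bears on the cost of the fix, not on the defect.

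**Conclusion.** The concern holds and should be fixed before the controls are drawn. That the two groups enter on different ventilation rules is plain from the text, and the control rule acts directly on one of the three primary outcome groups of the patient-outcome part.

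Confidence is high for the asymmetry and not for any particular net bias. With the floor alone, the spurious benefit to the robot at log-SD 0.8 runs from about 0.5 d at q = 5% to 1.4 d at q = 40%, and the rank-test false-positive rate from about 6% to 77%. These figures assume log-normal times, 30 patients per group, no true effect, and that ventilation in the control criterion means invasive ventilation. If unforeseen long-ventilation controls are admitted, size and direction cannot be determined from the protocol.

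**What to change.** 1. Reconcile the inclusion criteria and the historical-group list in section 7.2 with the statement on the comparison group in section 8, so that one ventilation criterion, knowable before the outcome, applies to both groups.
2. Select controls on preoperative information, that is, planned procedures for which more than 48 h of ventilation would have been expected, whatever the realised duration. The person selecting should preferably not see that duration.
3. Report for each group how many patients were ventilated for 48 h or less.
4. Add a comparison restricted to patients still ventilated at 48 h in both groups, as a sensitivity analysis only. Robot sessions may start before 48 h (sections 8 and 8.3 aim for the first 72 h), so this restriction conditions on a state that treatment may already have changed.

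**Cost.** One control criterion is reworded and the record query changes; no extra prospective patients are needed. Reconstructing the expected duration takes case-by-case judgement, and it must first be checked that the records allow it. The sensitivity analysis loses the share q of the robot group, for example 3 of 30 at q = 10%.
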